12.2.4 Listing of Adverse Events by Subject

All adverse events are listed by individual subject in [Listing 16.2.7.1](#).

12.3 Deaths, other Serious Adverse Events, and Other Significant Adverse Events

12.3.1 Listing of Deaths, Other Serious Adverse Events and Other Significant Adverse Events

12.3.1.1 Deaths

No subject died during the study ([Table 14.3.18](#)).

12.3.1.2 Other Serious Adverse Events

At least 1 serious TEAE was reported by 14 (7.0%) subjects in the udenafil group and 10 (5.0%) subjects in the placebo group ([Table 32](#)). Serious TEAEs reported by at least 2 subjects included chest pain (2 udenafil subjects), influenza (2 udenafil subjects), syncope (2 placebo subjects) and dyspnoea (1 udenafil subject and 1 placebo subject). All other serious TEAEs were reported by a single subject each.

Hospitalization was reported for 23 subjects (14 udenafil, 9 placebo) during the study ([Table 14.3.18](#)). Hospitalized subjects are identified in [Listing 16.2.7.3](#). No transplants were reported during the study ([Table 14.3.18](#)). Tabular summaries of transplants and hospitalizations by weight tertile are provided in [Table 14.3.19A](#), [Table 14.3.19B](#), and [Table 14.3.19C](#). Tabular summaries of transplants and hospitalizations by age tertile are provided in [Table 14.3.20A](#), [Table 14.3.20B](#), and [Table 14.3.20C](#).

Table 32: Serious Treatment-emergent Adverse Events Reported for ≥2 Subjects (Safety Population)

System Organ Class Preferred Term	Udenafil (N=200) n (%)	Placebo (N=200) n (%)
Subjects with ≥1 serious TEAE	14 (7.0)	10 (5.0)
General disorders and administration site conditions	2 (1.0)	1 (0.5)
Chest pain	2 (1.0)	0
Infections and infestations	2 (1.0)	3 (1.5)
Influenza	2 (1.0)	0
Nervous system disorders	2 (1.0)	5 (2.5)
Syncope	0	2 (1.0)
Respiratory, thoracic and mediastinal disorders	3 (1.5)	1 (0.5)
Dyspnoea	1 (0.5)	1 (0.5)

TEAE=treatment-emergent adverse event

Source: [Table 14.3.10](#)Program: [14_3_ae_tables.sas](#)

Six subjects (4 udenafil, 2 placebo) had serious TEAEs that were considered related to study drug ([Table 14.3.11A](#)). In the udenafil group, drug-related serious TEAEs included anxiety and bronchospasm reported in 1 subject and diplegia, retinal vascular occlusion, and palpitations reported in 1 subject each. In the placebo group, 2 subjects experienced a drug-related serious TEAE of syncope. Serious adverse events considered not related to study drug by the Investigator are summarized in [Table 14.3.11B](#). All serious TEAEs are listed in [Table 33](#).

A short description is provided below for each drug-related serious TEAE.

12.3.1.3.2 Adverse Events of Special Interest

Adverse events of hypotension (eg, blood pressure decreased, blood pressure diastolic decreased, blood pressure systolic decreased, hypotension, procedural hypotension), loss of consciousness, dizziness (eg, dizziness, dizziness exertional, procedural dizziness), presyncope, and syncope (syncope, syncope vasovagal) were identified in the SAP for separate summarization. Hypotension, dizziness, and syncope have been reported with other PDE-5 inhibitors (Pfizer 2017); loss of consciousness can be associated with these events.

At least 1 TEAE of special interest was reported by 18 (9.0%) subjects in the udenafil group and 19 (9.5%) subjects in the placebo group (Table 37). The incidence of individual TEAEs was similar between treatment groups.

Table 37: Number (Percent) of Subjects Reporting Treatment-emergent Adverse Events of Special Interest (Safety Population)

System Organ Class Preferred Term	Udenafil (N=200) n (%)	Placebo (N=200) n (%)
Subjects with \geq 1 TEAE of special interest	18 (9.0)	19 (9.5)
Dizziness	17 (8.5)	18 (9.0)
Loss of consciousness	0	1 (0.5)
Syncope	1 (0.5)	3 (1.5)

TEAE=treatment-emergent adverse event

Source: [Table 14.3.15](#)

Program: [14_3_ae_tables.sas](#)

The incidence of TEAEs of special interest was generally similar across age and weight tertiles. Tabular summaries of TEAEs of special interest by weight tertile are provided in [Table 14.3.16A](#), [Table 14.3.16B](#), and [Table 14.3.16C](#). Tabular summaries of TEAEs of special interest by age tertile are provided in [Table 14.3.17A](#), [Table 14.3.17B](#), and [Table 14.3.17C](#).

12.3.2 Narratives of Deaths, Other Serious Adverse Events and Certain Other Significant Adverse Events

Individual subject narratives for serious TEAEs, TEAEs resulting in discontinuation of study drug, and TEAEs of special interest are provided in [Section 14.3.3](#).

12.3.3 Analysis and Discussion of Deaths, Other Serious Adverse Events and Other Significant Adverse Events

No subject died during the study. At least 1 serious TEAE was reported by 14 (7.0%) subjects in the udenafil group and 10 (5.0%) subjects in the placebo group. No individual serious TEAE was reported by >2 subjects in either treatment group. Hospitalization was reported for 23 subjects (14 udenafil, 9 placebo) during the study. No transplants were reported.

At least 1 TEAE leading to temporary or permanent discontinuation of study drug was reported by 18 (9.0%) subjects in the udenafil group and 13 (6.5%) subjects in the placebo group. Headache was the only TEAE leading to temporary or permanent discontinuation of study drug reported by >2 subjects in either treatment group (3 subjects each in the udenafil and placebo groups).

The percentage of subjects reporting at least 1 serious TEAE is summarized across subgroups defined by baseline age and weight tertiles in [Table 38](#). No specific serious TEAE was reported for more than 2 subjects each in the udenafil group. Due to low number of subjects reporting specific serious TEAEs, summaries of individual serious TEAEs across subgroups are not meaningful.

Table 38: Number (Percent) of Subjects Reporting at Least 1 Serious Treatment-emergent Adverse Event by Age and Weight Tertiles (Safety Population)

Subgroup:	Udenafil (N=200) n/N (%)	Placebo (N=200) n/N (%)
Age at baseline		
Low tertile	6/72 (8.3)	2/61 (3.3)
Medium tertile	2/62 (3.2)	3/72 (4.2)
High tertile	6/66 (9.1)	5/67 (7.5)
Weight at baseline		
Low tertile	7/75 (9.3)	1/59 (1.7)
Medium tertile	3/68 (4.4)	5/64 (7.8)
High tertile	4/57 (7.0)	4/77 (5.2)

n=number of subjects with at least 1 serious adverse event; N=number of subjects in subgroup;

%=(n divided by N) × 100

Source: [Table 14.3.12A](#), [Table 14.3.12B](#), [Table 14.3.12C](#), [Table 14.3.13A](#), [Table 14.3.13B](#), and [Table 14.3.13C](#)
Program: [T_14_3_ae_tables.sas](#)

12.4 Clinical Laboratory Evaluation

12.4.1 Listing of Individual Laboratory Measurements by Subject and Each Abnormal Laboratory Value

Results for alanine aminotransferase, aspartate aminotransferase, and creatinine are listed by subject and study visit in [Listing 16.2.8.2](#).

12.4.2 Evaluation of Each Laboratory Parameter

12.4.2.1 Laboratory Values Over Time

Mean changes in alanine aminotransferase, aspartate aminotransferase, and creatinine from baseline to Week 26 were small and similar between treatment groups ([Table 39](#)).

Table 39: Changes in Safety Laboratory Values from Baseline to Week 26 (Safety Population)

	Udenafil (N=200)		Placebo (N=200)		LS Mean Difference (SE)
	N	Mean (SD)	N	Mean (SD)	
ALT (U/L)					
Baseline ^a	200	35.07 (14.287)	200	34.88 (14.552)	0.20 (1.444)
Week 26	189	35.08 (14.282)	192	35.93 (14.925)	-0.84 (1.499)
Difference, Week 26 – baseline	189	-0.34 (11.104)	192	0.73 (10.126)	-1.01 (1.018)
AST (U/L)					
Baseline ^a	200	32.57 (12.091)	200	32.15 (12.050)	0.41 (1.206)
Week 26	189	32.58 (11.542)	193	33.06 (15.350)	-0.48 (1.390)
Difference, Week 26 – baseline	189	-0.08 (9.154)	193	0.75 (14.538)	-0.70 (1.156)
Creatinine (mg/dL)					
Baseline ^a	200	0.68 (0.142)	200	0.72 (0.141)	-0.03 (0.014)
Week 26	189	0.74 (0.162)	192	0.76 (0.149)	-0.02 (0.016)
Difference, Week 26 – baseline	189	0.06 (0.098)	192	0.04 (0.113)	0.01 (0.011)

ALT=alanine aminotransferase; AST=aspartate aminotransferase; LS=least squares; SD=standard deviation; SE=standard error

a Baseline value was defined as the last assessment on or before dosing at baseline visit.

Source: [Table 14.3.21](#)

Program: [T_14_3_21.sas](#)

12.4.2.2 Individual Subject Changes

The percentages of subjects with a shift in alanine aminotransferase, aspartate aminotransferase, or creatinine from within normal limits at baseline to above the upper limit of normal at postbaseline were low and similar between treatment groups ([Table 40](#)). No subject met criteria for Grade 3 toxicity ($>5 \times$ upper limit of normal) for alanine aminotransferase or aspartate aminotransferase ([Listing 16.2.8.2](#)).

Table 40: Shifts from Within Normal Limits at Baseline to Above Upper Limit of Normal at Postbaseline (Safety Population)

Laboratory Parameter	Udenafil n/N (%)	Placebo n/N (%)
ALT	2/189 (1.1)	1/192 (0.5)
AST	5/189 (2.6)	4/193 (2.1)
Creatinine	0/189	0/192

ALT=alanine aminotransferase; AST=aspartate aminotransferase; n=number of subjects with at least 1 shift; N=number of subjects with data at baseline and postbaseline; %=(n divided by N) \times 100

Source: [Table 14.3.22](#)

Program: [T_14_3_22.sas](#)

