9.3.2 Exclusion Criteria

Subjects were excluded if they met any of the following criteria:

1. Weight <40 kg.
2. Height <132 cm.
3. Hospitalization for acute decompensated heart failure within the last 12 months.
4. Current intravenous inotropic drugs.
5. Undergoing evaluation for heart transplantation or listed for transplantation.
6. Diagnosis of active protein-losing enteropathy or plastic bronchitis within the last 3 years or a history of liver cirrhosis.
7. Known Fontan baffle obstruction, branch pulmonary artery stenosis, or pulmonary vein stenosis resulting in a mean gradient of >4 mmHg between the regions proximal and distal to the obstruction as measured by either catheterization or echocardiography, obtained prior to screening for the study.
8. Single lung physiology with greater than 80% flow to one lung.
9. Maximal VO₂ less than 50% of predicted for age and gender at enrollment.
10. Severe ventricular dysfunction assessed qualitatively by clinical echocardiography within 6 months prior to enrollment.
11. Severe valvar regurgitation, ventricular outflow obstruction, or aortic arch obstruction assessed by clinical echocardiography within 6 months prior to enrollment.
12. Significant renal (serum creatinine >2.0 mg/dL), hepatic (serum aspartate aminotransferase and/or alanine aminotransferase >3 times upper limit of normal), gastrointestinal or biliary disorders that could impair absorption, metabolism or excretion of orally administered medications, based on laboratory assessment 6 weeks prior to screening for the study.
13. Inability to complete exercise testing at baseline screening.
14. History of PDE-5 inhibitor use within 3 months before study onset.

15. History of any other medication for treatment of pulmonary hypertension within 3 months before study onset.
16. Known intolerance to oral udenafil.
17. Frequent use of medications or other substances that inhibit or induce cytochrome P450 (CYP)3A4.
18. Current use of alpha-blockers or nitrates.
19. Ongoing or planned participation in another research protocol that would either prevent successful completion of planned study testing or invalidate its results.
20. Noncardiac medical, psychiatric, and/or social disorder that would prevent successful completion of planned study testing or would invalidate its results.
21. Cardiac care, ongoing or planned, at a non-study center that would impede study completion.

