6.5.3 Clinical Laboratory Tests

Laboratory values will be converted to the project-defined unit of measurement before analysis.

Clinical laboratory variables will be presented in 2 ways. First, change from baseline to Visit 4 (study completion) will be summarized descriptively for each treatment group. The baseline value will be defined as the last assessment on or before dosing at Visit 1.

CONFIDENTIAL

Second, the number and proportion of subjects with treatment-emergent abnormal laboratory values will be tabulated and the subjects identified. Treatment-emergent abnormal laboratory tests are those in which the baseline value is normal (within the laboratory normal reference range) and post-baseline value is abnormal (i.e., meets Grade III or Grade IV toxicity criteria from the National Cancer Institute Common Terminology Criteria. All laboratory values obtained after Visit 1 will be included in the analysis.

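### Table 40 divides normal-to-high ALT and AST shifts by all subjects with paired data, so subjects raised at baseline can only lower the rate, and their worsening short of 5 × ULN is not tabulated by arm

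*Protocol*

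**What the plan says.** - **Numerator.** Protocol Section 12.4.2.2 describes the Table 40 event as a shift "from within normal limits at baseline to above the upper limit of normal at postbaseline were low and similar between treatment groups".
- **Denominator.** The Table 40 footnote defines N as "N=number of subjects with data at baseline and postbaseline". The Ns are 189 on udenafil for all three analytes. On placebo they are 192 for ALT and creatinine and 193 for AST.
- **Planned rule.** SAP 6.5.3 states: "Treatment-emergent abnormal laboratory tests are those in which the baseline value is normal (within the laboratory normal reference range) and post-baseline value is abnormal". Abnormal there meant Grade III or IV toxicity, and no denominator is given. Protocol Section 9.8.2.3 records that, after the blind was broken, the toxicity-grade rule was replaced by the normal-to-above-normal shift.
- **Entry limit.** The hepatic part of exclusion criterion 12 (Protocol Section 9.3.2) reads "hepatic (serum aspartate aminotransferase and/or alanine aminotransferase >3 times upper limit of normal". The criterion is applied "based on laboratory assessment 6 weeks prior to screening for the study", whereas Table 39 takes as baseline the last value on or before dosing.
- **Other coverage.** Section 12.4.2.2 says that no subject reached Grade 3 (above 5 × ULN) for ALT or AST. Table 39 gives mean changes, and Listing 16.2.8.2 lists every value by subject.

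**The concern.** A rate for a normal-to-high shift should be taken over the subjects who can make that shift. In Table 40, a subject already above ULN at baseline adds one to N and can add nothing to n, however far the value then rises. Entry allowed such subjects, and criterion 12 uses an earlier sample, so it does not strictly cap the Table 40 baseline either.

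Two things follow. The printed ALT and AST percentages are too low by an unreported amount if anyone was raised at baseline. And subjects with existing elevation, who matter for hepatic safety, have no by-arm count of individual worsening. As an illustration only, a rise from 1.5 to 4 × ULN would enter neither Table 40 nor the Grade 3 statement. Sections 12.6 and 13 conclude that there were no clinically important laboratory differences, and Table 40 is the only by-arm summary of individual laboratory changes shown in support.

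**Working it through.** **1. Reproduce Table 40** (100 × n/N, udenafil v placebo).
- ALT: 2/189 = 1.06% v 1/192 = 0.52% (printed 1.1 and 0.5).
- AST: 5/189 = 2.65% v 4/193 = 2.07% (printed 2.6 and 2.1).
- Creatinine: 0/189 v 0/192.

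All the percentages reproduce.

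**2. Identify the denominator.** The numbers of subjects with a change from baseline in Table 39 are 189/192 (ALT), 189/193 (AST) and 189/192 (creatinine). The Table 40 Ns are identical, so nobody was removed for being raised at baseline. N is all subjects with paired data, not the 200 randomized per arm and not the subjects normal at baseline.

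**3. Recompute on an at-risk denominator.** The number normal at baseline is not reported, so the share f raised at baseline is an assumption. Rate = n / [N × (1 − f)], with the denominator rounded to whole subjects:

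| f | ALT udenafil | ALT placebo | AST udenafil | AST placebo |
|---|---|---|---|---|
| 0% | 2/189 = 1.06% | 1/192 = 0.52% | 5/189 = 2.65% | 4/193 = 2.07% |
| 5% | 2/180 = 1.11% | 1/182 = 0.55% | 5/180 = 2.78% | 4/183 = 2.19% |
| 10% | 2/170 = 1.18% | 1/173 = 0.58% | 5/170 = 2.94% | 4/174 = 2.30% |

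Creatinine is zero for any f. At f = 10%, about 19 subjects per arm leave the denominator (189 − 170, 192 − 173, 193 − 174).

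**4. Let f differ between arms**, 10% in one and 0% in the other. The ALT difference (udenafil minus placebo) lies between 1.06 − 0.58 = 0.48 and 1.18 − 0.52 = 0.66 percentage points. The AST difference lies between 2.65 − 2.30 = 0.35 and 2.94 − 2.07 = 0.87. On the printed counts, Fisher's exact test gives p = 0.62 for ALT and 0.75 for AST.

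**5. Is 0 to 10% a reasonable range?** This is a rough model check. Inputs are the Table 39 means and SDs at baseline and Week 26. The correlation comes from the SD of change: r = (s₁² + s₂² − s_d²)/(2 s₁ s₂). For ALT on udenafil, (14.287² + 14.282² − 11.104²)/(2 × 14.287 × 14.282) = 0.698. A normal and a log-normal model were each fitted, with one ULN at both visits, solved separately in each arm so that the predicted shift rate equals the printed one. The implied share raised at baseline is:
- ALT: about 1.5% on udenafil and 0.5–0.6% on placebo.
- AST: about 5.2–5.4% on udenafil and 0.4–0.7% on placebo.

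The implied ULNs differ between arms (ALT 66–76 v 73–88 U/L; AST 52–55 v 64–73 U/L), so the model is only indicative. All the implied shares lie within 0 to 10%.

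**The case against.** The strongest reply is that this is a disclosed presentation choice. The footnote states N, every percentage reproduces, and SAP 6.5.3 specifies no denominator that could be wrong. Raised subjects are also covered elsewhere: Table 39 includes everyone with paired data and shows mean changes of −0.34 v 0.73 U/L for ALT and −0.08 v 0.75 U/L for AST (udenafil v placebo), the Grade 3 check applies to everyone, and all values are listed. All of this stands, and it limits the point. It does not close the gap: means can hide individual worsening, the Grade 3 statement begins only above 5 × ULN, and a listing is not a summary by arm.

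Four stronger readings are tempting, and the documents do not support them.
- **Many subjects were raised at baseline.** With Table 39 means near 35 U/L, a reader might assume a ULN of 40 to 50. The log-normal model then puts 29.8% to 13.5% of udenafil subjects above ULN for ALT. But the same model predicts 0.107 × 189 ≈ 20 to 0.065 × 189 ≈ 12 ALT shifts on udenafil, against 2 reported, and 0.108 × 192 ≈ 21 to 0.068 × 192 ≈ 13 on placebo, against 1. A share that large conflicts with Table 40 itself.
- **The kidney rate is diluted too.** Creatinine has no shifts, so its rate is zero on any denominator. The 3 × ULN allowance concerns transaminases only.
- **The SAP's normal-baseline condition hid severe cases.** That rule needed Grade III or IV, and no subject reached Grade 3 for ALT or AST, so it missed none for these analytes.
- **The extension study repeats the problem.** The Synopsis lists adverse events, vital signs and concomitant medication as the extension's interim safety criteria. No extension laboratory table is shown, so nothing can be said about one.

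**Conclusion.** The mismatch between numerator and denominator is established by the Table 40 footnote and the Table 39 Ns. So is the absence of any by-arm count of worsening from a raised baseline short of 5 × ULN. The size of the dilution is not established, because the ULN and the number raised at baseline are not reported. If everyone was normal at baseline, it is zero.

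Assuming 0 to 10% raised, the largest change to any printed rate is about 0.3 percentage points (AST on udenafil, 2.65% to 2.94%). The report's statement that the percentages "were low and similar between treatment groups" survives on either denominator. A reader might infer that a hepatic signal has been concealed; nothing in the documents shows a subject who worsened from a raised baseline. This is a minor point about denominator and completeness, not an error of arithmetic.

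**What to change.** In Table 40, and as a stated rule in SAP 6.5.3:
1. Set N for the normal-to-high shift to subjects within normal limits at baseline who have a postbaseline value.
2. Report by arm the number above ULN at baseline, for each analyte.
3. Add a baseline-by-postbaseline shift table by arm for ALT and AST, with categories normal, >ULN to 3 ×, >3 to 5 × and >5 × ULN, so that worsening from a raised baseline is counted.

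The values are already held in Listing 16.2.8.2. The cost is one reprogrammed table, and the printed percentages will rise slightly if anyone was raised at baseline. If few were, the report's conclusion is better supported than it is now.

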12.5 Vital Signs, Physical Findings and other Observations Related to Safety

Mean changes from baseline in blood pressure and heart rate were small and generally similar between treatment groups ([Table 41](#)). Statistically significant treatment group differences were observed for change in diastolic blood pressure from baseline to Week 2 and to Week 26, with greater decreases in the udenafil group.

Table 41: Changes in Blood Pressure and Heart Rate from Baseline to Week 2, Week 13, and Week 26 (Safety Population)

	Udenafil (N=200)	Placebo (N=200)	p-value^a
Systolic blood pressure (mmHg)			
Baseline ^b	n=200	n=200	
Mean (standard deviation)	112.32 (12.136)	113.21 (12.887)	0.477
Week 2 – baseline ^c	n=154	n=155	
Mean (standard deviation)	-1.34 (14.846)	-0.64 (15.424)	0.682
Week 13 – baseline ^c	n=131	n=143	
Mean (standard deviation)	-1.15 (13.000)	-1.26 (13.978)	0.948
Week 26 – baseline	n=189	n=190	
Mean (standard deviation)	-1.90 (12.166)	-0.49 (11.535)	0.246
Diastolic blood pressure (mmHg)			
Baseline ^b	n=200	n=200	
Mean (standard deviation)	68.39 (9.508)	69.30 (10.142)	0.355
Week 2 – baseline ^c	n=154	n=154	
Mean (standard deviation)	-4.34 (12.113)	-1.46 (12.398)	0.040
Week 13 – baseline ^c	n=131	n=143	
Mean (standard deviation)	-3.75 (11.374)	-1.95 (12.695)	0.220
Week 26 – baseline	n=189	n=190	
Mean (standard deviation)	-3.01 (9.644)	0.05 (10.696)	0.004
Heart rate (bpm)			
Baseline ^b	n=200	n=200	
Mean (standard deviation)	87.52 (15.253)	88.12 (14.128)	0.683
Week 2 – baseline ^c	n=154	n=155	
Mean (standard deviation)	-6.90 (13.464)	-8.30 (14.810)	0.385
Week 13 – baseline ^c	n=131	n=143	
Mean (standard deviation)	-6.94 (15.606)	-7.83 (14.230)	0.621
Week 26 – baseline	n=189	n=190	
Mean (standard deviation)	-1.06 (12.725)	-1.02 (12.448)	0.977

a P-value was assessed using analysis of variance with fixed factor for treatment group.

b Last pre-drug administration measurement.

c Collection of blood pressure and heart rate at Week 2 and Week 13 was stopped in the middle of the study and removed from the protocol version 3.0 (31 August 2017).

Source: [Table 14.3.23](#)

Program: [T_14_3_23.sas](#)

The percentages of subjects with potentially clinically significant vital sign values pre-6-minute walk and post-6-minute walk on Day 1 were small and similar between treatment groups. Potentially clinically significant vital sign changes on Day 1 are

summarized in [Table 42](#). There were no TEAEs for blood pressure or heart rate associated with these changes. Vital sign results for individual subjects are presented in [Listing 16.2.8.1](#).

Table 42: Potentially Clinically Significant Vital Sign Changes on Day 1 (Safety Population)

Vital Sign Time Point	Udenafil (N=200)	Placebo (N=200)
Low systolic blood pressure, n (%) with postdose value ≤ 80 mmHg and decreased ≥ 20 mmHg from value before dosing		
Pre-6MWT ^a	0	0
Post-6MWT ^a	0	0
≥ 1 event at either time point	0	0
High systolic blood pressure, n (%) with postdose value ≥ 140 mmHg and increased ≥ 20 mmHg from value before dosing		
Pre-6MWT ^a	0	0
Post-6MWT ^a	11 (5.5)	8 (4.0)
≥ 1 event at either time point	11 (5.5)	8 (4.0)
Low diastolic blood pressure, n (%) with postdose value ≤ 50 mmHg and decreased ≥ 15 mmHg from value before dosing		
Pre-6MWT ^a	2 (1.0)	2 (1.0)
Post-6MWT ^a	2 (1.0)	3 (1.5)
≥ 1 event at either time point	4 (2.0)	4 (2.0)
High diastolic blood pressure, n (%) with postdose value ≥ 100 mmHg and increased ≥ 15 mmHg from value before dosing		
Pre-6MWT ^a	0	1 (0.5)
Post-6MWT ^a	1 (0.5)	0
≥ 1 event at either time point	1 (0.5)	1 (0.5)
Low heart rate, n (%) with postdose value ≤ 45 bpm and decreased ≥ 15 bpm from value before dosing		
Pre-6MWT ^a	0	0
Post-6MWT ^a	1 (0.5)	0
≥ 1 event at either time point	1 (0.5)	0
High heart rate, n (%) with postdose value ≥ 130 bpm and increased ≥ 15 bpm from value before dosing		
Pre-6MWT ^a	0	0
Post-6MWT ^a	5 (2.5)	4 (2.0)
≥ 1 event at either time point	5 (2.5)	4 (2.0)

6MWT=6-minute walk test

a Approximately 2 hours after first drug administration.

Source: [Table 14.3.24](#)

Program: [T_14_3_24.sas](#)

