9.7.1.5 Safety Evaluations

Safety assessments were summarized for the Safety population. No formal hypothesis testing was performed.

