6.0 Statistics

All statistical tests will be at the 0.05 alpha level, 2-tailed, unless stated otherwise. Probabilities will be rounded to 4 decimal places before assigning statistical significance.

Descriptive statistics for categorical endpoints will include the number and percent of subjects in each treatment group and category. Quantitative endpoints will be summarized for each treatment group with the mean, median, standard deviation, minimum value, and maximum value.

Individual subject data will be presented in data listings, which will include normal reference ranges when appropriate.

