6.4.2 Secondary Efficacy Endpoints

Secondary efficacy endpoints include change from baseline to Visit 4 (Week 26) in:

- Exercise capacity
 - Minute oxygen consumption at the ventilator anaerobic threshold (VAT)
 - Ventilatory equivalents of carbon dioxide (VE/VCO₂) at VAT
 - Respiratory rate and minute ventilation at peak exercise
 - Maximal work rate
 - Work rate at the VAT
- Ventricular performance
 - Myocardial performance index (MPI) determined by velocities obtained from blood pool Doppler assessment of the inflow and outflow tract of the dominant ventricle. It is the primary performance endpoint of the echocardiogram.
 - Ventricular cavity size, eccentricity, and mass (based on echocardiogram)
 - Systolic function estimate using mean dP/dt during isovolumetric contraction (dP/dt_{ic}) and peak systolic annular velocity (S') on tissue Doppler
 - Qualitative and quantitative estimate of atrioventricular valve insufficiency
- Endothelial function: log-transformed reactive hyperemia index (lnRHI), as measured by pulse amplitude tonometry (PAT) testing using the EndoPAT® device
- Natural logarithm transformation of BNP
- Functional health status as measured by the full scale PedsQL
 - Physical functioning score

CONFIDENTIAL

- Psychosocial functioning score
- Cardiac-specific quality-of-life score
- Pediatric Cardiac Quality of Life Inventory (PCQLI) score

Each secondary efficacy endpoint will be summarized descriptively by treatment group.

Treatment group differences for endpoints associated with the PedsQL and PCQLI will be assessed with Friedman's test using ventricular morphology (single left versus single right or mixed) as the stratification factor. The treatment group difference for the qualitative estimate of atrioventricular valve insufficiency will be assessed with a Cochran-Mantel-Haenszel test using ventricular morphology (single left versus single right or mixed) as the stratification factor.

The remaining secondary efficacy endpoints will be analyzed with the ANCOVA model with fixed factors for ventricular morphology (single left versus single right or mixed) and treatment group with a covariate for the baseline value.

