6.5 Safety Evaluations

Safety assessments will be summarized for the Safety Population. No formal hypothesis testing will be performed.

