6.5.4 Vital Signs

Change from baseline (last value before dosing at Visit 1) to each scheduled assessment will be summarized descriptively by treatment group for each vital sign variable.

Vital signs that are potentially clinically significant will be identified with the criteria in Table 2 and summarized descriptively by treatment group. Baseline will be defined as the last vital sign value obtained before the first dose of study drug.

Table 2 Criteria for Potentially Clinically Significant Vital Signs

Vital Sign	Criterion	Definition of Potentially Clinically Significant Value
Systolic blood pressure	Low	Value \leq 80 mmHg and decreased \geq 20 mmHg from value before dosing
	High	Value \geq 140 mmHg and increased \geq 20 mmHg from value before dosing
Diastolic blood pressure	Low	Value \leq 50 mmHg and decreased \geq 15 mmHg from value before dosing
	High	Value \geq 100 mmHg and increased \geq 15 mmHg from value before dosing
Pulse	Low	Value \leq 45 bpm and decreased \geq 15 bpm from value before dosing
	High	Value \geq 130 mmHg and increased \geq 15 mmHg from value before dosing

bpm = beats per minute

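### Table 41 tests vital-sign change without the baseline value and prints bare p-values; the diastolic difference should be shown baseline-adjusted with an interval

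*Protocol*

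**What the plan says.** The SAP planned no inference here. Section 6.5 states "No formal hypothesis testing will be performed", and Section 6.5.4 says that change "to each scheduled assessment will be summarized descriptively by treatment group for each vital sign variable". The Protocol document, which reports the completed study, repeats this in Section 9.7.1.5: "No formal hypothesis testing was performed".

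Table 41 in Section 12.5 nevertheless prints a p-value for each variable at each time point. Its footnote reads "P-value was assessed using analysis of variance with fixed factor for treatment group". The text above the table opens with "Mean changes from baseline in blood pressure and heart rate were small and generally similar between treatment groups". The next sentence reports significant diastolic differences at Weeks 2 and 26, with the larger falls on udenafil. Section 12.6 concludes that vital signs showed no clinically important difference between arms.

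Weeks 2 and 13 are incomplete: "Collection of blood pressure and heart rate at Week 2 and Week 13 was stopped in the middle of the study".

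For most secondary efficacy change scores, SAP Section 6.4.2 specifies ANCOVA with morphology and "treatment group with a covariate for the baseline value". The primary endpoint (SAP Section 6.4.1) has the same structure. Nothing similar is specified for vital signs.

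**The concern.** Change from baseline correlates negatively with baseline, so a model that omits baseline leaves explainable variation in the error term. It also leaves any chance baseline difference in the estimate. Here udenafil started lower in diastolic pressure. Regression to the mean then works against showing a fall on udenafil.

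Blood pressure is not an incidental safety variable in this trial. Section 12.3.1.3.2 lists hypotension, dizziness and syncope as events of special interest because they are reported with other drugs of the class. Section 9.4.7 notes small pressure decreases when udenafil is combined with certain antihypertensives. A reader needs the size of the effect and its uncertainty to judge the summary wording. Table 41 gives arm means and a p-value, and the reader must work out the rest. Table 39, for laboratory values, does the reverse: it prints a least-squares difference with its standard error and no p-value.

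**Working it through.** **Inputs (Table 41, diastolic pressure, mmHg).** Baseline: 68.39 (SD 9.508) on udenafil and 69.30 (SD 10.142) on placebo, n=200 each. Change, mean (SD), n:

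| Visit | Udenafil | Placebo | Printed p |
|---|---|---|---|
| Week 2 | -4.34 (12.113), 154 | -1.46 (12.398), 154 | 0.040 |
| Week 13 | -3.75 (11.374), 131 | -1.95 (12.695), 143 | 0.220 |
| Week 26 | -3.01 (9.644), 189 | 0.05 (10.696), 190 | 0.004 |

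**Step 1: reproduce the printed p-values.** With two groups, one-way ANOVA is the pooled-variance t-test, with SE = SDpooled × √(1/n1 + 1/n2).

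| Visit | Difference | SDpooled | SE | 95% CI | p |
|---|---|---|---|---|---|
| Week 2 | -2.88 | 12.26 | 1.40 | -5.63 to -0.13 | 0.0401 |
| Week 13 | -1.80 | 12.08 | 1.46 | about -4.7 to 1.1 | 0.219 |
| Week 26 | -3.06 | 10.18 | 1.05 | -5.12 to -1.00 | 0.0037 |

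The baseline difference is -0.91 (p=0.355, as printed). All match within rounding.

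**Step 2: ANCOVA from summary statistics.**
- cov = (SDbase² + SDvisit² - SDchange²)/2, and r = cov/(SDbase × SDvisit)
- slope of change on baseline: b = cov/SDbase² - 1
- adjusted difference = raw difference - b × baseline difference
- residual SD = SDvisit × √(1 - r²)

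Two inputs are not printed and have to be assumed: the SD at each visit, and the baseline means of the subjects measured at each visit. The base case takes SDvisit equal to the pooled baseline SD (9.83) and a baseline difference of -0.91.

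**Step 3: Week 26.** cov = (96.63 + 96.63 - 103.73)/2 = 44.77, so r = 0.46 and b = -0.54. Adjusted difference = -3.06 - (0.54 × 0.91) = -3.55. Residual SD = 9.83 × √(1 - 0.463²) = 8.71, which gives SE 0.90, 95% CI -5.31 to -1.79, p=0.0001.
- SDvisit at 0.9 to 1.1 times baseline: -3.6 to -3.5, with the SE 21% to 9% smaller.
- SDvisit from 8.5 to 12 mmHg: -3.66 to -3.33.
- Baseline difference of the 379 measured subjects varied over a 95% sampling range (-1.36 to -0.46): -3.79 to -3.30.
- Adjustment enlarges the difference as long as b is negative, that is, while SDvisit is below √(96.63 + 103.73) = 14.2 mmHg.

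**Step 4: Week 2.** The base case gives -3.59 (95% CI -5.74 to -1.44), p=0.001. Over SDvisit 8.5 to 12, p runs from 0.0001 to 0.008. Over a subset baseline difference of -1.96 to 0.14, p runs from 0.0001 to 0.012.

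**Step 5: Week 13.** The base case gives -2.49 (-4.76 to -0.22), p=0.032, but it is fragile. If the 274 measured subjects are treated as random draws from each arm, the sampling SD of their baseline difference is 9.83 × √(1/131 - 1/200 + 1/143 - 1/200) = 0.67. The range is then -0.91 ± 1.96 × 0.67, or -2.22 to 0.40.

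| Subset baseline difference | SDvisit / SDbase | Adjusted difference | p |
|---|---|---|---|
| -2.22 | 1.0 | -3.48 | 0.003 |
| -0.91 | 1.0 | -2.49 | 0.032 |
| -0.50 | 1.0 | -2.18 | 0.060 |
| 0 | 1.0 | -1.80 | 0.12 |
| 0.40 | 1.0 | -1.50 | 0.195 |
| -0.91 | 1.31 | -2.16 | 0.12 |

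The last row is the SD ratio at which the Week 13 correlation equals the 0.46 derived for Week 26. The change SDs are larger at Weeks 2 and 13 (12.3 and 12.1) than at Week 26 (10.2). Either weaker correlation or more variable readings would produce that, and the printed data cannot separate the two.

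**Step 6: other variables.** In the base case, systolic pressure and heart rate stay above p=0.05 at all visits. The smallest is systolic pressure at Week 26 (adjusted -1.81, p about 0.09).

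**The case against.** The strongest reply is that nothing planned was breached and nothing was concealed. The SAP asks only for descriptive vital-sign summaries and reserves baseline-adjusted ANCOVA for efficacy. An adjusted analysis would be as unplanned as the ANOVA. That stands, and it is why the result must be labelled not pre-specified.

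A reader might infer that the table masks a steady effect. It does not. Larger diastolic falls on udenafil are printed at all three visits, and the sentence after the general summary reports Weeks 2 and 26 as significant.

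A reader might also call the unadjusted comparison biased. Under randomisation it is unbiased on average, and the 0.91 mmHg imbalance is chance. What can be said is that, given this imbalance, the estimate is probably too small.

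It is fair, too, that related safety data show no divergence. Low-diastolic events on Day 1 were 4 in each arm (Table 42). Special-interest events were 9.0% versus 9.5%, with no hypotension listed (Table 37). The documents also give no evidence that morphology predicts blood pressure, so the gain from adding it is unquantified.

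None of this answers the remaining point. The table gives a p-value where a descriptive analysis should give a difference and an interval, and it leaves unused a covariate that was collected on everyone.

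**Conclusion.** The point holds as a matter of precision and reporting. Week 26, where 379 of 400 subjects were measured, is the firm case: about -3.5 mmHg adjusted against -3.06 raw. This rests on a visit SD close to the baseline SD and on the measured subjects having nearly the full-sample baseline difference. Week 2 stays below p=0.05 throughout the ranges tried.

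It is tempting to conclude that Week 13 turns significant and that a uniform reduction at every visit is thereby shown. The documents do not support that. With the subset baseline difference varied at equal SDs, the adjusted Week 13 difference runs from about -1.5 to -3.5 mmHg and p from about 0.003 to 0.195. A larger visit SD alone can also keep p above 0.05. No stated significance finding at Weeks 2 or 26 is overturned. What needs attention is the summary wording, which a reader cannot weigh without an effect size.

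**What to change.** Re-run Table 41 as ANCOVA on change, with the baseline value of the same variable and the morphology stratum, as in the efficacy models. At each visit, print the adjusted difference with its 95% CI in place of the bare p-value. Print also the baseline means of the subjects contributing to that visit, so that the Week 2 and Week 13 subsets can be judged. State that the analysis was not pre-specified. Then reconcile the opening summary in Section 12.5, and the matching conclusion in Section 12.6, with a diastolic difference of roughly 3 mmHg. Take the figure from the re-run table and do not fix one in the text beforehand.

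The cost is one model change in one table program and a few sentences of text. No new data are needed.
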